6.2.5 Dropouts and missing data

If a subject's data for a given planned visit is missing due to the actual visit having occurred outside the specified visit interval, data from the actual visit will be used for imputing data for the planned visit, if the time difference between the planned and actual visit no more than twice the tolerance for that visit. Otherwise, data will be imputed following the process for other types of missing data. See Figure 1 in section 2 for the visit timings and tolerance intervals.

In the primary evaluation, the flowing efficacy analyses will be conducted with missing data imputed using multiple imputation:

1. Supine slow vital capacity (SVC) through 12 weeks
2. Combined assessment of function and survival (CAFS) through 48 weeks
3. Time to respiratory event
4. Clinical Global Impression (CGI) through 48 weeks
5. Supine Borg CR 10 scale at 12 weeks
6. Slope of change in the ALSFRS-R respiratory domain through 48 weeks

For each imputed endpoint, 10 independent imputed data sets will be generated using the fully conditional specification (FCS) method. Predictive mean meatching will be used to impute continuous variables, and logistic regression methods for classification variables, as appropriate.

The imputation models will include measurements of the endpoint being imputed from all planned visits at which it should be collected, from the baseline visit up to the week 48 visit. The measurements are used in a one-row-per-subject format, by which all other visits' data are used to impute missing data at all visits. Further, the imputation model will also include time-invariant variables used in the statistical models or potentially associated with the missing outcome: treatment group, randomisation strata (site of onset, edaravone use, and region; as collected on the CRFs), sex, age group (< 65, 65–74, ≥ 75), and riluzole use status.

SAS code in the following fashion will be used to perform the imputation process:

```
proc mi nimpute = 10 seed = 270815;  
  class ARM STRATAV SEX AGEGR1 RILUZUSE;  
  var ARM STRATAV SEX AGEGR1 RILUZUSE AVAL1-AVAL8;  
  fcs regpmm (/ k = 5) logistic;  
run;
```

To ensure reproducibility of the imputation results, the randomly chosen seed value of 270815 will be used for all imputation procedures.

Imputation will be done directly based on the collected values, and derived quantities used for the analyses, like e.g. change from baseline, will be calculated after the imputation process,

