6.2.14 Subgroups

Subgroups will be analysed for evidence of a differential treatment effect. A treatment-by-subgroup interaction term will be added to the statistical model, and the stratification factor, if present, will be removed. Subgroups defined by the following variables will be investigated:

1. Age (< 65, 65–74, ≥ 75)
2. Sex (male, female)
3. Race (white, non-white)
4. Country
5. Region (North America, rest of the world)
6. Site of onset (bulbar, spinal)
7. Edaravone use (yes, no)
8. Riluzole use (yes, no)
9. Combination of edaravone and riluzole use (4 groups)
10. Below median disease duration (time from symptom onset to randomization)
11. Above median time from symptom onset to diagnosis
12. Acetylation status (slow, fast; see 7.7)
13. Renal impairment status (see 7.9.3)
14. Hepatic impairment status (see 7.9.3)
15. Below median SVC (sitting) at screening
16. Below median SVC (supine) at baseline
17. King's clinical stage at baseline (see 7.5.2.1)
18. Below median ALSFRS-R at baseline
19. ALS progression rate at baseline (< 1 point/month, ≥ 1 point/month)
20. ALS progression rate at baseline (observed tertiles)
21. Dose change category (see section 7.4)

Subgroup analyses will be performed for the primary efficacy endpoint, the time to respiratory event endpoint, and the slope of change in the ALSFRS-R total score endpoint. Ad-hoc analyses of other endpoints may also be performed, and included in the study report.

Summary of AEs and AESIs will be presented in the subgroups of: age; sex; race; BMI; edaravone use; riluzole use; acetylation status; baseline medical history groups of interest (see 7.3); baseline renal and hepatic impairment status; and baseline King's clinical stage.

Adverse events will be summarised by patients having heart rate increase related dose changes. Drug-drug-interactions with medication groups of interest (see 7.10.1) will be evaluated for blood pressure, pulse rate, and QT interval. Dose changes will be further presented by acetylation status.

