Primary efficacy will be evaluated based on the fitted model, using contrasts to obtain an estimate of the difference between the treatment and placebo at the Week 12 visit (Visit 5). Statistical significance of the Week 12 treatment difference will be tested. All SVC measurements from planned study visits prior to the Week 12 visit will be included in the estimation of the model.

SAS code in the following fashion will be used to perform the computations:

```
proc mixed data = ADEFF order = data alpha = 0.05 covtest;
  where ITTFL = "Y" and PARAMCD = "SVCPPSUP" and
    AVISIT in ("Week 2", "Week 4", "Week 8", "Week 12");
  class TRTP(ref = "PLACEBO") AVISIT STRATAR USUBJID SITEID;

  model CHG = BASE STRATAR TRTP AVISIT TRTP * AVISIT / ddfm = KR;
  repeated AVISIT / subject = USUBJID type = UN R;
  random SITEID / type = VC;

  estimate "Treatment Difference at Week 12"
    TRTP 1 -1 TRTP * AVISIT 0 0 0 1 0 0 0 -1 / cl;
run;
```

In the primary analysis, missing data are imputed using multiple imputation. As a result, the analysis above is repeated for each of the imputed data sets with the use of a by-statement. The analysis results are then pooled for inference according to the methods described in 6.2.5.

In additional analyses, data from all planned visits through 48 weeks will be included in the MMRM, and the treatment effect will be estimated with contrasts at each study visit. Further, a random slope model will be fitted, with visits' actual study days replacing the visit factor.

Changes in SVC (supine) between the last measurement while on treatment and the post-treatment measurement from their End of Study visit will be described.

Subgroup analyses will be conducted by removing the randomization stratum effect from the primary analysis model, and including the subgroup term and its interaction with treatment.

Descriptive statistics of SVC (supine) will also be presented by visit, treatment group, and angle of measurement position. The angle is categorised into three groups: 1) completely flat (0 degrees); 2) slightly elevated (up to 15 degrees); 3) unable to perform supine (> 15 degrees). The effect of angle of measurement will also be explored in an additional analysis, where the angle will be included as a factor in the primary analysis MMRM.

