7.10.3 COVID-19

The number of subjects affected with any changes to study visit procedures, the number of protocol deviations, and study visits performed as a telephone contact rather than a protocol-specified on-site visit due to COVID-19 will be summarized by treatment group with descriptive statistics.

Both confirmed and suspected infections of COVID-19 will be reported as adverse events. The number of affected subjects will then be found as part of regular AE reporting (see 7.9.2).

In addition to appearing in standard reporting, protocol deviations and AEs related to COVID-19 will also be summarised in a dedicated section.

We expect precautionary measures to result in an increase of missing data for the remainder of the study. This will primarily affect Week 48 visits, and particularly measurements that cannot be performed over the phone, such as the SVC. Missing data due to COVID-19 will be treated the same as other missing data, following the procedures specified in in 6.2.5.

Efficacy measurements that were collected after the World Health Organization declared the COVID-19 outbreak a pandemic on March 11, 2020 will be flagged in the data. The potential impact of the pandemic on the treatment effect will be evaluated by including a term for whether the measurement was taken before or after the pandemic declaration in the MMRM for SVC and for ALSFRS-R. These analyses will be performed without any missing data imputation. Descriptive statistics for SVC and ALSFRS-R will be reported by visit, treatment group, and timing with respect to the pandemic declaration.

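### The supine SVC subgroup interactions appear to be tested on data imputed without an arm-by-subgroup term, which biases them modestly towards no difference

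*SAP*

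**What the plan says.** **Imputation.** SAP 6.2.5 uses fully conditional specification with predictive mean matching: "fcs regpmm (/ k = 5) logistic". The variable list is "var ARM STRATAV SEX AGEGR1 RILUZUSE AVAL1-AVAL8": arm, the combined stratum, sex, age group, riluzole use and the endpoint at eight visits. There is no product term, and imputation is not done separately by arm. The subject's other visits do enter: "The measurements are used in a one-row-per-subject format, by which all other visits' data are used to impute missing data at all visits". The same section sends the imputed data through the endpoint methods of section 7.

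**Subgroups.** SAP 6.2.14 lists 21 subgroup variables and says: "A treatment-by-subgroup interaction term will be added to the statistical model". On scope it says: "Subgroup analyses will be performed for the primary efficacy endpoint, the time to respiratory event endpoint, and the slope of change" (of the ALSFRS-R total score). For SVC, 7.5.1.1 says: "Subgroup analyses will be conducted by removing the randomization stratum effect from the primary analysis model, and including the subgroup term". The treatment-by-subgroup product is added too. That section runs the primary analysis on multiply imputed data.

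**Where imputation is switched off.** 7.10.3 says of the COVID-19 models: "These analyses will be performed without any missing data imputation". 7.5.4.4 plans a repeat without imputation of the efficacy analyses that used it. Neither section names the subgroup models, and 6.2.14 does not say which data they use.

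**The concern.** A multiple-imputation analysis gives sound estimates of a term only if the imputation model allows for that term. Here the subgroup model estimates a treatment-by-subgroup interaction, while the imputation model gives arm one coefficient for everyone. Imputed records therefore carry less subgroup difference than real ones, and the pooled interaction moves towards zero.

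Many of the variables are also missing as main effects. Of the 21 in 6.2.14, 13 are not in the SVC imputation list: race, country, disease duration, time to diagnosis, acetylation status, renal and hepatic status, sitting SVC, King's stage, baseline ALSFRS-R, the two progression-rate splits and dose change category. Yet 6.2.5 sets out to include time-invariant variables that the statistical models use.

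At stake is how a finding of consistent effects across subgroups is read. The bias runs in that direction, and the interaction estimates are already imprecise.

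**Working it through.** **1. The plan's own figure.** SAP section 5: difference 3.6, SD 10, two-sided 5%, 90% power. n per group = 2(1.960 + 1.282)² × 10² / 3.6² = 162.2, so 163 by the normal approximation. The noncentral t gives 90.2% power at 164, which reproduces the stated 164 per group. After 20% loss, 2:1 leaves 240 and 120 subjects (power 89.5%). The documents give no figure for subgroup interactions, for the correlation between visits or for the share missing at Week 12.

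**2. Precision of an interaction.** Two equal subgroups among 240 and 120 give cells of 120, 120, 60 and 60. Unadjusted SE = 10 × √(2/120 + 2/60) = 2.24 points.

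**3. How much shrinkage to expect.** Let m be the share missing at Week 12 and r the share of the true interaction that imputed values keep. The share kept overall is then about 1 − m(1 − r). Simulation supplied r, using the SAP's method (predictive mean matching, k = 5, eight visits, main effects of arm and subgroup). Assumptions not in the documents: equal subgroups, true effects of 0 and 7.2 (mean 3.6), and dropout completely at random.

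| Adjacent-visit correlation, dropout, effect | m | r | 1 − m(1 − r) | Simulated share kept |
|---|---|---|---|---|
| 0.7, spread, constant | 0.10 | 0.376 | 0.938 | 0.937 |
| 0.7, spread, constant | 0.20 | 0.400 | 0.880 | 0.880 |
| 0.9, spread, constant | 0.20 | 0.611 | 0.922 | 0.922 |
| 0.5, spread, constant | 0.20 | 0.245 | 0.849 | 0.850 |
| 0.7, spread, building up | 0.20 | 0.179 | 0.836 | 0.838 |
| 0.7, baseline only, constant | 0.10 | 0.065 | 0.907 | 0.907 |
| 0.7, baseline only, constant | 0.20 | 0.012 | 0.802 | 0.804 |

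The formula matches the simulation, and the shrinkage cannot much exceed the missing fraction.

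**4. A second set-up.** 450 subjects 2:1, interaction 4 points, dropout spread evenly over Weeks 2-12, normal regression imputation from arm and earlier SVC, and Week 12 analysis of covariance. The share kept was 0.95 (constant effect) and 0.92 (growing effect) with 10% missing, and 0.92 and 0.84 with 20%. Steps 3 and 4 together give about 5-8% shrinkage with 10% missing (9% if all dropouts have baseline only) and 8-20% with 20%.

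**5. The model as planned.** 7.5.1.1 adds subgroup and treatment-by-subgroup without a visit term, so one interaction is shared by Weeks 2-12. Under that repeated-measures model, with the second set-up and correlations of 0.7-0.9, shrinkage was 3-4% (10% missing) and 5-7% (20%) for a constant effect, and 5-7% and 8-12% for a growing one. There were only 100 trials per scenario. The growing-effect figures are the least certain and depend on the assumed correlation pattern.

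**6. Size in points.** For a 4-point interaction, the 5-16% of step 4 is 0.2-0.6 points, against an SE of about 1.6-2.0 in that set-up.

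**7. Effect of the repair.** N = 450, 20% missing, correlation 0.7, 10 imputations, 192 trials, true interaction 7.2, Week 12 estimate. Main-effects imputation gave 6.32 (6.32/7.2 = 0.88). With arm-by-subgroup added it gave 7.14. Rejection rates were 85% and 87%. The simulation SE of each is about √(0.86 × 0.14/192) = 2.5 percentage points, so no power difference is shown.

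**The case against.** The strongest objection is that the SAP never says subgroup models use imputed data. It ties imputation to the primary evaluation, and 7.5.1.1 borrows the primary model without naming a data set. The sensitivity analyses in 7.5.4.7, 7.5.4.8 and 7.5.4.11 do say to impute where applicable; 6.2.14 does not. If the subgroup analyses are imputed, 7.5.4.4 read literally already yields an observed-data repeat. This stands in part: the point rests on the natural reading, and at the least the wording is unclear. But 7.5.4.4 does not name subgroups, and it is a sensitivity analysis, not the reported result.

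Four stronger readings are tempting, and the documents do not support them:

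- *Every imputed value assumes the same drug effect in all subgroups.* Observed visits feed the imputation and carry part of the subgroup effect: about 0.4 of it in the base case of step 3, and close to none only when there is no post-baseline visit.
- *The tests lose power.* Step 7 does not show this.
- *Time to respiratory event is biased in the same way.* It is on the imputation list, but 6.2.5 censors one day after treatment discontinuation and Table 2 censors study discontinuation at the last assessment. Values imputed after dropout should contribute little, and no calculation was made.
- *All subgroup tests are affected.* The ALSFRS-R total-score slope is not on the imputation list; only the respiratory-domain slope is.

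Also fair is that an observed-data model is not a perfect reference. With a growing effect, the planned single-interaction model on observed data fell 2-5% below its complete-data value.

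**Conclusion.** The point holds as a minor one. If the SVC subgroup models are fitted to the imputed data, the interaction they estimate is missing from the imputation model, and it is biased towards zero in every scenario examined. With dropout spread over Weeks 2-12, the model as planned loses about 3-7% with 10% missing and 5-12% with 20%. The Week 12 interaction loses about 5-8% and 8-20%, where the 20% is the extreme case of no post-baseline data in any dropout.

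The 20% missing rate borrows the plan's total dropout allowance, so the Week 12 rate may well be lower. The bias is small beside the standard error of any single interaction. SAP 7.5.2 treats analyses outside the hierarchy as supportive, so neither the primary result nor the hierarchical tests change.

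**What to change.** Add a sentence to SAP 6.2.14 stating which data the subgroup models use. Either:

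1. fit the SVC subgroup models to observed data by the repeated-measures model without imputation, as 7.5.4.4 and 7.10.3 do for other analyses; or
2. for each subgroup run, add the subgroup variable and its product with ARM to the imputation model.

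Apply the same rule to time to respiratory event wherever imputed values enter it.

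Option 1 needs only wording, since 7.5.4.4 already calls for the observed data. Its downside is that overall and subgroup estimates then rest on different handling of missing data. Option 2 keeps the handling aligned and recovered the interaction in step 7, at the price of a separate imputation run per subgroup variable.

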5. DETERMINATION OF SAMPLE SIZE

Sample size estimation is based primarily on supine SVC results from the study 3119001 LEVALS (Table 1). LEVALS had placebo-controlled data only up to 2 weeks, and therefore extrapolation of the results was needed. The placebo effect from phase II tirasemtiv trial BENEFIT-ALS (Shefner JM et al., 2016) was also evaluated.

Assuming a difference of at least 3.6% in change from baseline supine SVC between treatment groups and a common standard deviation of 10%, 164 evaluable subjects per group in a 1:1 allocation ratio have 90% power to detect a statistically significant difference in a two-sided, 5% α -level, two group T-test. Using a 2:1 allocation ratio, randomisation of 450 subjects to the study (approximately 300 levosimendan and 150 placebo treated subjects) allows for a total dropout rate of approximately 20%.

Table 1. Mean (SD) change from baseline SVC (supine) %-predicted in LEVALS

Treatment	2 weeks	12 weeks
Levosimendan 1 mg x 2	+2.4 (8.3)	-4.9
Levosimendan 1 mg x 1	+0.8 (8.6)	
Placebo	-3.6 (9.4)	-17.7 ¹
Placebo (BENEFIT-ALS)	-1.4	-8.5

¹ Extrapolated from the data

SD = standard deviation

Based on the dexpramipexole phase III study EMPOWER (Cudkowicz ME et al., 2013), a 12 point reduction in total ALSFRS-R score and a 15% mortality rate at 12 months can be assumed

in placebo treated patients. Assuming a 10 point decline in ALSFRS-R, with a standard deviation of 8 points, and a 20% relative improvement in survival, 450 patients provide approximately 80% simulated power to detect a statistically significant difference using a joint rank test. With 450 subjects and assuming a 48-week levosimendan event rate of 73% and hazard ratio of 0.70, time to respiratory event has approximately 70% power to detect a statistically significant difference using a log-rank test.

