6.2.2 Significance level and confidence intervals

Two-sided tests with a significance level of 5% will be used throughout the analyses. Corresponding 95% confidence intervals will be calculated for model-based contrasts, comparing the active treatment to placebo, using model-based standard error estimates.

The study has interim analyses that allow early stopping for futility, but not for efficacy. Therefore, we do not make adjustments to the significance levels in the final analyses.

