within each imputed data set. For questionnaires that consist of multiple sub-items, values for individual items will be imputed, and the summary scores that are used for analysis purposes will be re-calculated based on the imputed data. Imputation is not done directly on the summary scores—which will have missing values if even one of their sub-items has a missing value—in order to maximise the use of collected information.

Multiply-imputed data will be analysed according to the methods specified for each endpoint in section 7, with the addition of performing the analysis separately in each imputed data set with the use of a by-statement in the analysis procedure. Results of all the analyses are then saved, and pooled estimates are calculated for inference purposes.

Pooled estimates of model parameters are to be obtained, depending on the analysis method, with SAS code in the following fashion:

```
proc mianalyze parms = parms covb(effectvar = rowcol) = covb;  
  class TRTP VISIT;  
  modeleffects TRTP VISIT TRTP * VISIT;  
run;
```

Above, the `parms` and `covb` data sets are obtained from the corresponding `solution` and `covb` outputs from the `proc mixed` procedure. The exact statements and options used for the pooling procedure will vary based on the analysis model used.

Model-based contrasts obtained with estimate statements will also be pooled, however the method used differs slightly from the one used for model parameters:

```
proc mianalyze data = estimates;  
  modeleffects estimate;  
  stderr stderr;  
  by label;  
run;
```

The method above will also be used to analyse hazard ratios from Cox models for time-to-event endpoints, with parameter estimates from `proc phreg` as the estimates data. For CAFS, Hodges-Lehmann estimates for median difference will be pooled in the same manner.

A complete-case analysis will be performed as a sensitivity analysis, using observed data only. There, listwise deletion will be used to select subject-visit records for fitting the model, removing subject-visits records from the analysis if any of the variables used contains a missing value.

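### Imputing each ALSFRS-R item from its own history and then summing makes imputed scores too narrow; the respiratory-domain slope test is likely to run at about 6-7% instead of 5%

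*SAP*

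**What the plan says.** SAP 6.2.5 (Dropouts and missing data) lists six analyses that use multiple imputation. They include CAFS through 48 weeks and the slope of the ALSFRS-R respiratory domain, the first and fifth endpoints in the hierarchy of SAP 6.2.3.

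- **Unit of imputation:** "For questionnaires that consist of multiple sub-items, values for individual items will be imputed". Scores are then re-built from the imputed items. The SAP's reason is that a summary score is lost when even one item is missing, so working on items uses more of the collected data.
- **Predictors:** "The imputation models will include measurements of the endpoint being imputed from all planned visits at which it should be collected", plus treatment group, strata, sex, age group and riluzole use.
- **Sample code:** one outcome series, "var ARM STRATAV SEX AGEGR1 RILUZUSE AVAL1-AVAL8", with predictive mean matching (k = 5) and 10 imputations. It is offered as a pattern, not as final code.
- **Use:** SAP 7.5.2.2 ranks survivors on change in the ALSFRS-R total and judges significance from the Hodges-Lehmann interval. SAP 6.2.5 pools those estimates over imputations. The slope endpoint uses the sum of items 10-12.

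Neither the text nor the code names the other items as predictors. No sentence says that they are left out.

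**The concern.** When a subject drops out, all 12 items are missing together. In reality they tend to fall together. If each is drawn separately from its own past, the draws are nearly independent given that past, and their high and low values partly cancel in the sum. The imputed total or domain score then has too little spread. Imputations that vary too little from one data set to the next give too small a between-imputation variance, and Rubin's rules then give too small a standard error.

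The same model also falls short of the SAP's own aim. If one item is missing at an attended visit, the 11 items observed at that visit are not used.

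At stake are the precision claimed for CAFS and the error rate of the respiratory-domain slope test.

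**Working it through.** **Inputs from the documents**
- Test level (SAP 6.2.2): "Two-sided tests with a significance level of 5% will be used throughout the analyses".
- Size and allocation (SAP 5): 450 subjects, 300 to 150.
- Placebo course (SAP 5): "a 12 point reduction in total ALSFRS-R score and a 15% mortality rate at 12 months can be assumed".
- Active course (SAP 5): "Assuming a 10 point decline in ALSFRS-R, with a standard deviation of 8 points, and a 20% relative improvement in survival". Mortality is read as 15% x (1 - 0.20) = 12%.
- Items are integers 0-4. Protocol Table 1 gives ten ALSFRS-R time points: visits 1 and 3-8 (seven) and three telephone calls.
- Imputation: predictive mean matching, k = 5, m = 10.

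**Assumed, because not given:** the correlation between item changes and the ALSFRS-R missingness at Week 48. The 20% dropout in SAP 5 belongs to the SVC sizing.

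**The plan's own figure.** No standard error or imputed SD is stated for any ALSFRS-R endpoint. The only CAFS figure is about 80% simulated power. From the stated inputs a joint rank simulation gives 0.67, so that figure did not reproduce. The settings behind it are not given, this is a separate matter, and nothing below uses it.

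**Step 1: mechanism.** For k items of equal variance and correlation r, the variance of the sum is k x var x [1 + (k - 1)r]. Independent draws give k x var. The SD ratio is 1/sqrt[1 + (k - 1)r].
- Total, k = 12, r = 0.37: 1/sqrt(5.07) = 0.44.
- Respiratory domain, k = 3, r = 0.47: 1/sqrt(1.94) = 0.72.

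These illustrate the case in which an item's past tells nothing. Observed histories are correlated and carry part of the correlation into the sum, so the actual loss is smaller.

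**Step 2: spread of the imputed total** (MAR dropout 25%, mean item correlation 0.37; true SD in dropouts 7.98)

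| Imputation | SD of imputed Week 48 change | Ratio |
|---|---|---|
| Item from own history | 5.65 | 0.71 |
| Item given the other items | 7.36 | 0.92 |
| Total imputed directly | 7.94 | 0.99 |

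Over dropout of 15-40% and correlation of 0.23-0.50, the own-history ratio is 0.66-0.75, that is, 25-34% too low.

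**Step 3: CAFS.** Pooled variance = W + (1 + 1/10)B. In the same scenario:
- Own history: sqrt(13.93² + 1.1 x 2.97²) = 14.27 (mean over runs 14.26).
- Total: sqrt(13.83² + 1.1 x 4.61²) = 14.65 (mean over runs 14.63).

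W hardly moves, because CAFS is a rank score and its overall spread is fixed by the number of subjects. Only B shrinks.

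Under the null (1,100 trials, 25% dropout), SE/empirical SD is 14.03/15.04 = 0.93 for own history and 14.53/14.31 = 1.02 for the total. Type I error is 4.7% and 3.9% (Monte Carlo SE 0.6 points). A separate 2,000-trial null simulation with 26% missing and five visits gave a ratio of 0.92, or 0.96 when the SAP's fixed seed is restarted for each item, and again 4.7%.

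With a normal statistic a ratio of 0.93 would mean 2 x [1 - Φ(1.96 x 0.93)] = 6.8%. The 4.7% is therefore an observation, not a derivation. The Hodges-Lehmann test also ran slightly low with complete data (ratio 0.99, type I error 4.4%).

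**Step 4: respiratory-domain slope under the null.** Ten time points, MAR dropout, subject-level slopes standing in for the random slope model, 8,000 trials per row (Monte Carlo SE about 0.25 points):

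| Missing at Week 48 | Item correlation | SE ratio, own history / domain sum | Type I error, own history / domain sum |
|---|---|---|---|
| 21% | 0.47 | 0.96 / 1.00 | 6.0% / 5.0% |
| 29% | 0.47 | 0.95 / 1.01 | 6.1% / 5.1% |
| 30% | 0.72 | 0.94 / 1.02 | 6.5% / 4.7% |

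The normal formula gives 6.0%, 6.3% and 6.5% for ratios 0.96, 0.95 and 0.94, which agrees with the simulated rates.

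A second set at 18-26% missing gave:
- own history: ratio 0.91-0.95, type I error 6.0-7.0%
- other items added to the model: 0.98-1.00, 5.2-5.4%
- domain sum imputed: 1.01, 4.7-4.8%.

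**The case against.** **The SAP does not say that items are modelled in isolation.** The code is a pattern, and its eight-value series fits the eight supine SVC visits, not the ten ALSFRS-R time points, so it must be adapted anyway. This stands in part: a shared item model is not excluded. But none is specified, and a programmer following the text would use each item's own history.

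**CAFS is not shown to be invalid.** A reader might infer that narrow imputed totals make the CAFS test reject too often, or that both variance components shrink. SAP 7.5.2.2 makes CAFS a rank score, so the within-imputation part is unaffected, and the test stayed at 4.7% in two simulations. This objection stands. It does not protect the slope, which is not a rank score.

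**Not all correlation is lost.** Correct. Correlated observed histories carry part of it, and only the residual part is dropped.

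**Less may be imputed than assumed.** ALSFRS-R can be taken by telephone and after treatment stops (Protocol 6.1.3, 6.1.6). This stands as a limit on size.

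**Checks exist.** SAP 7.5.4.4 repeats every imputed analysis without imputation, and tipping-point analyses will be considered. These may reveal sensitivity to missing data, but they do not correct the pooled standard error.

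**Item-level imputation has a purpose.** It uses partly completed questionnaires, and time to respiratory event needs items 10-12 separately. This stands, and it is why the preferred fix keeps imputation at item level.

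**Conclusion.** The point holds with a limited size. On the natural reading of SAP 6.2.5, imputed ALSFRS-R sums are under-dispersed. For the respiratory-domain slope this means a pooled standard error about 4-9% too small and a type I error of about 6-7%, given 18-30% missing at Week 48 and moderate to high item correlation. For CAFS the standard error is about 4-8% below the empirical SD. That affects the stated precision, and no excess of false positives was seen.

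The sizes depend on assumed item correlation, missingness and MAR dropout, and on a subject-level proxy for the random slope model. They would shrink with less missing data or weaker correlation. If the sponsor already intends a joint item model, the point reduces to stating so.

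**What to change.** In SAP 6.2.5, before unblinding, state that each ALSFRS-R item's imputation model also contains the other items at the same visit, or the sum of the other items in the total (for CAFS) or domain (for the slope). Give the ALSFRS-R code with its own ten time points. In simulation this brought the slope's type I error to 5.2-5.4%.

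Alternatively, fill isolated missing items from the items observed at the same visit, then impute the analysed score (total or respiratory domain) directly across visits. Keep item-level imputations for time to respiratory event.

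The cost is SAP wording and a modest program change, with no new data. The first option gives a larger model: all items at all time points make 12 x 10 = 120 variables for 450 subjects, against 3 x 10 = 30 for the respiratory domain alone, so the sum of the other items may be the practical choice for the total. The second option leaves item-level and score-level imputations that need not agree exactly.
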